The primary goal of this proposal is to determine the efficacy of tranexamic acid in reducing the rate of hematoma formation after breast reduction surgery. This will be a double-blinded, randomized controlled study. The research will be achieved by randomizing one breast in a bilateral breast reduction to receive topical tranexamic acid, while the other breast will not receive the study drug. Both the surgical team and the patient will be blinded to which side has received the study drug. The patient will then be followed for the standard postoperative period and the rate of hematoma development will be recorded. Patient demographics, comorbidities, treatment history, and surgical details will be collected from these charts and analyzed for their impact on perioperative blood loss. **We hypothesize that use of topical tranexamic acid will decrease the rate of hematoma formation and the rate of blood transfusion without increasing the incidence of deep vein thrombosis or thromboembolic events.**

b) Target Population and Recruitment Methods

Consecutive patients presenting for breast reduction mammoplasty performed by plastic surgeons affiliated with Montefiore Medical Center will be offered enrollment in the study. Potential study participants will be recruited at their preoperative consultation appointments that take place at the Hutchinson Metro Center campus. Written informed consent (detailed below) will be obtained from all participants before inclusion. As this proposal involves greater than minimal risk to patients, we will have a Data and Safety Monitoring Plan in place prior to beginning the study.

c) Inclusion and Exclusion Criteria

Inclusion criteria include: being over the age of 18 and being scheduled for reduction mammoplasty at the Hutchinson Metro Center campus of Montefiore Medical Center.

Exclusion criteria include: oncologic breast reductions, unilateral breast reductions, history of thromboembolic disease, history of bleeding diatheses, history of stroke, current pregnancy, severe comorbidity (defined as American Society of Anesthesiologists (ASA) fitness grade IV or above).

d) Primary and Secondary Outcomes

Primary outcome: development of hematoma within 30 days of surgery

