The primary objective of this pilot study is to explore whether, and to what extent, treatment using TXA decreases the risk of hematoma in patients undergoing breast reduction mammoplasty (BRM) compared to a saline placebo. A double-blind within-subjects design will be used with each patient receiving both treatments and thus serving as their own control. A simple randomization scheme will determine which treatment will be used for each side (left or right) for each patient. A Bayesian approach will be employed to estimate the posterior probability distribution of the

relative risk reduction in post-surgical hematoma between treatment rate between treatment with TXA and control. This posterior probability distribution provides the information necessary to answer the salient questions informative about the presence and strength of an efficacy signal for TXA; specifically, what is the probability that treatment with TXA reduces the risk of hematoma, compared to control by an amount δ for any $0 < \delta < 1$. Note that the probability that the relative risk < 1 corresponds to the probability that treatment with TXA is superior to the control. A description of this approach follows.

Prior to data collection and consistent with a null hypothesis of no difference between treatments we assume that the effect of treatment with TXA is equal to the effect of treatment with control. This assumption is formalized by assuming that the probability of developing a hematoma is the same for each treatment. The Bayesian approach considers this prior probability of developing a hematoma to be a random variable, which we specify to be a beta distribution with parameters 0.35 and 4.65, translating into a mean of 0.07 (the assumed hematoma rate for both treatments under the “null” hypothesis) and a standard deviation of about 0.10. Since patients will be treated with both treatments, the prior probabilities of developing a hematoma are not assumed to be independent. In our approach, we assume a conservative correlation of 0.30.

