This prior probability is combined with the observed data, the number of observed hematomas under each treatment (a binomial random variable) to yield an estimated posterior probability distribution for each hematoma rate. These estimated rates will be used to estimate the posterior distribution for the relative risk, and its natural logarithm which has the advantage of being approximately normally distributed and less skewed given the low expected hematoma rates.

An illustration of the estimated probability distribution for the natural logarithm of the relative risk is shown (left) under the “alternative” hypothesis that treatment with TXA reduces the rate of hematoma by a relative 50% compared to control based on a sample of 100 patients, the proposed sample size. The distribution is obtained by simulation using 100,000 replications. The sample size of 100 was chosen to ensure a high probability of detecting an efficacy signal (a relative risk of 0.5 or less) should it exist.

Specifically, with a sample size of 100, the probability of estimating a relative risk < 1 , or natural logarithm of the relative risk < 0 (i.e., estimating that treatment with TXA is superior to treatment with control) is approximately 80%, corresponding to an odds of 4:1. This 80% probability corresponds to the frequentist notion of power.

Note that the prior odds (assuming equal rates of hematoma) of observing a relative risk less than one is 1:1. Also, the probability of observing odds of 4:1 in favor of TXA under the assumption of equal hematoma rates using each treatment is approximately 20%. This 20% is a false positive rate corresponding to the frequentist Type I error rate.

We will perform a corresponding frequentist analysis using conditional logistic regression to estimate the odds ratio and corresponding 95% confidence interval for developing a hematoma using TXA compared to control. Our use of a non-informative prior ensures that these results will be consistent with those provided by the Bayesian approach, and thus enhance interpretation of the trial's results. Descriptive statistics, using both numerical and graphical summaries, will be used to describe the sample with respect to demographics, baseline characteristics, and important outcomes.

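### The plan claims about 80% power and about 20% Type I error but declares no success rule, and the two figures belong to different criteria

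*Combined protocol and SAP*

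**What the plan says.** All references are to the combined protocol and SAP.

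- **Aim.** Section 3 a) states: "The primary goal of this proposal is to determine the efficacy of tranexamic acid in reducing the rate of hematoma formation". Section 8 b) describes the same trial as an exploratory pilot and also says that 100 patients give adequate power.
- **Planned output.** Section 8 b) will estimate the posterior distribution of the RR and use it to ask "what is the probability that treatment with TXA reduces the risk of hematoma, compared to control by an amount" δ, where δ may be anything between 0 and 1. No δ and no required probability is chosen.
- **Power.** The sample of 100 was "chosen to ensure a high probability of detecting an efficacy signal (a relative risk of 0.5 or less) should it exist". The figure of about 80% is the stated probability of an estimated RR below 1, glossed as "estimating that treatment with TXA is superior to treatment with control". The same 80% is then equated both with odds of 4:1 and with frequentist power.
- **Type I error.** The figure of about 20% is "the probability of observing odds of 4:1 in favor of TXA under the assumption of equal hematoma rates", and the plan calls it a false positive rate.
- **Supporting analysis.** A conditional logistic regression will give an odds ratio with a 95% confidence interval. Its part in any verdict on efficacy is not stated.

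**The concern.** Power and Type I error are properties of a decision rule. The plan quotes both without saying which rule they describe, and it ties them to different events. A reader will take them as a pair: a trial that succeeds 80% of the time if TXA halves the hematoma rate, and 20% of the time if TXA does nothing. If no rule behaves like that, the sample size justification describes a test that will not be carried out.

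The final analysis is affected too. The criteria in section 8 b) can give different answers on the same counts, and nothing in the text says which one answers the primary hypothesis. The choice would then have to be made when the results are interpreted, and the chance of a false claim of efficacy depends on it.

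**Working it through.** **Inputs from section 8 b).** 100 patients, each with one TXA and one saline breast. Control rate: "translating into a mean of 0.07 (the assumed hematoma rate for both treatments under the" null hypothesis. Prior: "which we specify to be a beta distribution with parameters 0.35 and 4.65". Alternative: a 50% relative reduction, so 0.07 against 0.035. Correlation: "we assume a conservative correlation of 0.30".

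**Assumption.** The text does not say how the 0.30 enters the model. I therefore let the correlation between a patient's two outcomes be 0 or 0.30, and the correlation between the two posterior rates be 0 or 0.30 (Gaussian copula), giving four variants.

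**Prior.** Mean 0.35/(0.35 + 4.65) = 0.07. SD √[0.35 × 4.65/(5² × 6)] = √0.01085 = 0.104. Both agree with the plan.

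**Posterior.** With x hematomas among 100 breasts, each side has a Beta(0.35 + x, 104.65 − x) posterior. Odds of 4:1 mean P(RR<1) = 4/(4 + 1) = 0.80.

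**One result by hand: 5 TXA versus 7 saline.**
- Posterior means: 5.35/105 = 0.0510 and 7.35/105 = 0.0700. The estimated RR is below 1 (raw 5/7 = 0.71).
- Variances: 0.0510 × 0.9490/106 = 0.000456 and 0.0700 × 0.9300/106 = 0.000614. The SD of the difference is √0.00107 = 0.0327.
- z = 0.0190/0.0327 = 0.58, so P(RR<1) ≈ 0.72. Without the normal approximation it is 0.73 (independent posteriors) or 0.76 (correlation 0.30).
- Estimated RR<1 is met; 4:1 is not.

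**Operating characteristics.** I summed the paired multinomial probabilities over all count pairs up to 30 per side; simulation with 400,000 trials per scenario agrees. Estimated RR<1 means fewer hematomas on TXA than on saline. Tied counts give a posterior median RR of exactly 1, so they do not qualify; ties make up 11–13% of trials when TXA has no effect.

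| Correlation: outcomes / posterior | Average P(RR<1) at true RR 0.5 | Estimated RR<1: no effect / true RR 0.5 | 4:1 odds: no effect / true RR 0.5 |
|---|---|---|---|
| 0 / 0 | 0.79 | 44% / 83% | 21% / 63% |
| 0 / 0.30 | 0.81 | 44% / 83% | 25% / 67% |
| 0.30 / 0 | 0.81 | 43% / 88% | 17% / 66% |
| 0.30 / 0.30 | 0.83 | 43% / 88% | 21% / 70% |

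**Reproducing the plan's figures.** Each can be recovered, but from a different quantity.
- About 80% matches the average posterior P(RR<1) when the true RR is 0.5 (0.79–0.83). That is an average of posterior probabilities, not the frequency with which a rule is met.
- About 20% matches the frequency of reaching 4:1 when TXA has no effect (17–25%).
- The rule that gives about 20% false positives has 63–70% power. A rule of estimated RR<1 reaches 83–88% power at the price of 43–44% false positives.

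**How often the two criteria split.** Every result that reaches 4:1 also has estimated RR<1, so the split is the difference between the two columns. In the first variant with no effect it is 44.4% − 20.8% = 23.6%. Across variants it is 20–27% of trials with no effect and 16–22% with a true halving.

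**If RR 0.5 were a threshold for the estimate.** When the true RR is exactly 0.5, the posterior median RR is 0.5 or less in 46–47% of trials, and the raw ratio in 56–57%.

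**The case against.** Four points on the other side carry weight.

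1. **A rule is implied.** Calling 4:1 under equal rates a false positive presupposes that 4:1 is a positive. So one should not infer that the plan has no usable criterion. What remains is that the rule is not declared and that the quoted 80% is not its power.

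2. **RR 0.5 is probably not a pass mark.** A reader might infer a third, conflicting threshold from the sample size sentence. But its closing words refer to an effect that may or may not exist, and the preceding illustration uses a 50% reduction as the alternative. The natural reading is the assumed true effect. The phrase is ambiguous and needs rewording, but it does not establish a third rule.

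3. **A pilot may simply estimate.** Section 8 b) sets out to explore whether and how far TXA lowers the risk, and a posterior reported for every δ is a legitimate prespecified output with no binary verdict. This stands as a way to repair the plan. It does not defend the present text, because estimation alone has no power or Type I error.

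4. **The logistic regression is supportive.** It comes with a 95% interval and is offered as an aid to interpretation. The absence of a separate alpha is not a defect; only its role in the verdict needs stating.

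A reader might also infer that the investigators intend to choose a criterion after seeing the results. Nothing in the documents suggests this. The text leaves the choice open, and that is all that can be said.

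**Conclusion.** The point holds in this limited form: the plan quotes power and Type I error without declaring the rule they belong to, and no single rule considered here has both. The implied 4:1 rule has about 63–70% power and 17–25% false positives; estimated RR<1 has about 83–88% and 43–44%. The false positive rate therefore roughly doubles between the two criteria. They give opposite answers in about a fifth to a quarter of trials with no effect.

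These ranges rest on 100 analysable pairs, a 7% control rate, a true RR of 0.5 for power, the stated priors, and correlations of 0 to 0.30. The plan's own prior model could shift them, since the documents do not say how the 0.30 is applied. The mismatch is present in all four variants. The change should be made, but it does not call the within-patient design or the Bayesian approach into question.

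**What to change.** Amend section 8 b) before unblinding, in one of two ways.

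**(a) Declare the rule that the plan already implies.** For example: *An efficacy signal will be declared if the posterior probability that RR<1 is at least 0.80 (odds of at least 4:1).* Then:
- restate the power of that rule (about 63–70% here) and its false positive rate (about 17–25%), recomputed under the plan's actual prior model, and say how the 0.30 correlation enters;
- say that posterior probabilities for other δ values and the conditional logistic regression are supportive and cannot change the verdict;
- reword the sample size sentence so that RR 0.5 is the assumed true effect. If it is meant as a threshold for the estimate, report its own probability (about 46–57% at a true RR of 0.5).

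**(b) State that the pilot is estimation only.** Report the posterior distribution in full, and remove the claims of adequate power, of 80% power and of a 20% Type I error rate. Align the aim in section 3 a) with this.

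Either way the cost is a few sentences, with no extra patients or data. Under (a) the investigators give up free choice of δ and accept a less favourable stated power. Under (b) they give up a formal claim of efficacy from this trial.

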Subject treatment assignments will remain blinded until the final subject has completed follow up and all data has been recorded and validated. Urgent, immediate unblinding due to medical emergency may be authorized by the Investigator. When possible, the treatment assignment will be provided to the treating physician in order to maintain the blind for the Investigator and study staff.

8. Data Analysis

We hypothesize that use of topical tranexamic acid will decrease total perioperative blood loss, hematoma formation, and transfusion rates without increasing the incidence of deep vein thrombosis or thromboembolic events.

a) Chart review data:

Patient charts will be abstracted for baseline demographic data and medical comorbidities that may independently increase the risk of developing a postoperative hematoma. Data to be abstracted from the medical record includes: demographic data (including patient gender, age, ethnicity), medical data (including body mass index, comorbidities (e.g. hypertension, diabetes, hyperlipidemia, coronary artery disease), smoking history, history of neoadjuvant radiation therapy or chemotherapy, history of thromboembolic disease, bleeding diatheses, or use of anticoagulant medications), surgical data (including type of operation performed, surgical team involved, weights of tissue removed, estimated blood loss, drain outputs in the immediate postoperative period, date that drain(s) were removed) and complications within 30 days of the index operation including hematoma requiring operative washout or bedside evacuation, seroma, cellulitis, nipple-areolar complex necrosis, fat necrosis, delayed wound healing, deep vein thrombosis and pulmonary embolism. Patients with insufficient records or those who are lost to follow-up will be excluded from the final analysis.

b) Statistical Analysis

[figure not shown]
We have partnered with our institution's Department of Surgery faculty biostatisticians on the statistical methods for this proposal. **Based on a Bayesian approach, a sample size of 100 patients will be sufficient to adequately power this study.**

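### The 80% power and the 20% Type I error in section 8b belong to two different events, and no single event has both at the stated inputs

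*Combined protocol and SAP*

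**What the plan says.** All of this is in the Combined protocol and SAP, section 8 (Data Analysis), part b) Statistical Analysis.

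- The opening paragraph claims that "a sample size of 100 patients will be sufficient to adequately power this study".
- On the choice of size: "The sample size of 100 was chosen to ensure a high probability of detecting an efficacy signal", the signal being a relative risk (RR) of 0.5 or less.
- First figure, for a 50% relative reduction and 100 patients: the probability of an estimated RR below 1, glossed as "estimating that treatment with TXA is superior to treatment with control) is approximately 80" percent. The section equates this with odds of 4:1 and adds: "This 80% probability corresponds to the frequentist notion of power".
- Second figure: "the probability of observing odds of 4:1 in favor of TXA under the assumption of equal hematoma rates using each treatment is approximately 20" percent, followed by "This 20% is a false positive rate corresponding to the frequentist Type I error rate".
- Between the two, the section says that under equal rates the odds of an RR below 1 are 1:1.
- Prior: each hematoma probability is Beta(0.35, 4.65), with mean 0.07. On dependence, "the prior probabilities of developing a hematoma are not assumed to be independent", and "In our approach, we assume a conservative correlation of 0.30".

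**The concern.** Power is the chance that a given event occurs when the effect is real. Type I error is the chance that the same event occurs when there is no effect. Here the 80% is attached to an estimate falling below 1, and the 20% to posterior odds reaching 4:1, which is a stricter requirement. The section's own 1:1 statement puts the first event near 50% under equal rates, not 20%. It gives no probability at RR 0.5 for the second event.

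The two figures are the only numerical support for the statements that 100 patients is adequate and gives a high chance of finding a signal. A reader will take them as 80% power at a 20% false positive rate and will judge the trial, and a null result from it, on that basis.

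**Working it through.** **Inputs from section 8b**

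- n = 100 patients, each with one TXA breast and one control breast.
- Control rate 0.07. TXA rate 0.07 under equal rates, and 0.5 × 0.07 = 0.035 at RR 0.5.
- Prior Beta(0.35, 4.65): mean 0.35/5 = 0.07; SD √(0.35 × 4.65/(25 × 6)) = √0.01085 = 0.104. Both agree with the plan.
- Correlation 0.30, stated for the prior probabilities. The plan does not say whether it also applies to the two outcomes within a patient, so outcome correlations φ = 0 and φ = 0.30 are both shown.

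**Method**

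Each patient falls into one of four cells (hematoma on both sides, TXA side only, control side only, neither), with

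p11 = pT·pC + φ√(pT(1−pT)·pC(1−pC)).

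For φ = 0.30 this is 0.0049 + 0.30 × 0.0651 = 0.0244 under equal rates, and 0.00245 + 0.30 × 0.0469 = 0.0165 at RR 0.5. The exact joint distribution of the counts (xT, xC) over 100 patients follows. The posterior combines the two beta priors, linked by a Gaussian copula with parameter 0.30, with the two binomial likelihoods. The copula is an assumption, since the plan names no joint form. Raising its parameter to 0.373, so that the two rates themselves correlate at about 0.30, leaves the probabilities of reaching 4:1 unchanged to three decimals.

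**Can each stated figure be reproduced alone?**

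- The 20%: P(posterior odds ≥ 4:1) under equal rates is 0.206 (φ = 0) or 0.163 (φ = 0.30). The first agrees.
- The 80% as worded: P(xT < xC) at RR 0.5 is 0.832 (φ = 0) or 0.875 (φ = 0.30), somewhat above 80%.
- The 80% as an average: the mean of the posterior P(RR < 1) over trials at RR 0.5 is 0.79 to 0.81 with prior correlation 0 or 0.30. This agrees, but it is an expected posterior probability and not power. Its value under equal rates is 0.50.

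**How far apart are the two events?**

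Take 7 control hematomas, the expected number:

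| TXA hematomas | Estimated RR < 1? | Posterior P(RR < 1) | Odds |
|---|---|---|---|
| 6 | yes | 0.612 | 0.612/0.388 = 1.6:1 |
| 5 | yes | 0.723 | 0.723/0.277 = 2.6:1 |
| 4 | yes | 0.823 | 0.823/0.177 = 4.7:1 |

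Six is enough for the first event. The second needs four or fewer.

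**Both probabilities for the same event**

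| Event | Setting | At RR 0.5 | Equal rates |
|---|---|---|---|
| Stated in the plan | – | 80% | 20% |
| Estimated RR < 1 | φ = 0 | 83% | 44% |
| Estimated RR < 1 | φ = 0.30 | 88% | 43% |
| Odds ≥ 4:1 | priors 0.30, φ = 0 | 62% | 21% |
| Odds ≥ 4:1 | priors 0.30, φ = 0.30 | 63% | 16% |
| Odds ≥ 4:1 | independent priors, φ = 0 | 63% | 21% |
| Odds ≥ 4:1 | independent priors, φ = 0.30 | 66% | 17% |

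Ties (xT = xC) count as not below 1. Under equal rates they have probability 0.111 (φ = 0) or 0.134 (φ = 0.30). Splitting them evenly gives 0.444 + 0.111/2 ≈ 0.50 and 0.433 + 0.134/2 = 0.50, which is the plan's own 1:1.

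As a sensitivity check only, since the plan does not describe it, imposing 0.30 on the posterior instead gives 67%/25% (φ = 0) and 70%/21% (φ = 0.30) for the 4:1 event.

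**Does another cut-off rescue the pair?**

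The cut-off on P(RR < 1) was moved from 0.40 to 0.96 in every reading above. The first cut-off with at most 20% under equal rates gives 60–67% at RR 0.5. The highest cut-off that keeps at least 80% at RR 0.5 gives 32–37% under equal rates.

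**The case against.** The best defense is that the 80% was never meant as the chance of an estimate below 1. The section illustrates one distribution of the log relative risk at RR 0.5 and equates 80% with odds of 4:1. It then asks how often 4:1 is reached under equal rates. Read this way, the 80% is the average posterior probability that RR is below 1, and both numbers reproduce. This reading fits the arithmetic better than the literal wording and may well be what was simulated. The illustrating figure is not available to settle it. It is also why the criticism is of pairing and labeling and does not allege a miscalculation. It does not rescue the label: an average posterior probability is not the chance of reaching 4:1, and its counterpart under equal rates is 50%.

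A second objection is that only the readings with 0.30 on the priors follow the text. That is fair, and 62–63% with 16–21% is the result to weigh most. The other readings show only that the conclusion does not depend on this choice.

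Third, the section calls this a pilot, sets no success rule, and states the 1:1 odds openly. That limits the consequence. It does not make the terms power and Type I error correct where the plan chose to use them.

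**Conclusion.** The concern holds. The 80% is not the power of the event that carries the 20%. On the plan's own placement of the 0.30, the chance of reaching 4:1 at RR 0.5 is 62–63%, about 17 to 18 points below the stated 80%, with 16–21% under equal rates. The event to which the plan attaches the 80% has 43–44% under equal rates, or about 50% with ties split.

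This rests on fixed true rates of 7% and 3.5%, 100 evaluable pairs, the stated prior, and outcome correlations of 0 and 0.30. That two events are involved is plain from the text and needs no calculation.

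The error is confined to the stated operating characteristics. The planned posterior analysis and the conditional logistic regression remain valid. It should still be corrected, because the claim that the size is adequate has no other numerical basis.

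**What to change.** In section 8b, give both probabilities, at RR 0.5 and at RR 1, for one event from the same simulation, and say whether the 0.30 enters through the prior, the outcomes or both. If the event is posterior odds of at least 4:1, suitable text would be:

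> With 100 patients, the probability of posterior odds of at least 4:1 in favor of TXA is [rerun value] if TXA halves a 7% hematoma rate and [rerun value] if the rates are equal.

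With 0.30 on the priors, expect about 62–63% and 16–21%. Alternatively, remove the power and Type I error labels altogether, since a pilot needs no success rule. Either way, delete the sentence that equates the 80% with power. If the sponsor confirms that the 80% is the average posterior probability of RR < 1 at RR 0.5, label it so and give its value under equal rates, 50%.

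In the opening paragraph of 8b, replace the claim of adequate power with a statement that 100 is a pilot size with the operating characteristics given below it.

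The cost is one rerun of the existing simulation and a few sentences. The stated power will look less favorable. No patients are added, and neither the design nor the primary analysis changes.
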